### **4.4. Early Withdrawal of Participants**

#### **4.4.1. When and How to Withdraw Participants**

Participants with severe psychological symptoms (e.g., suicidal thoughts), those who fail to adhere to protocol requirements, and those who withdraw consent will be withdrawn from the

CONFIDENTIAL

This material is the property of the University of Pennsylvania. Do not disclose or use except as authorized in writing by the study sponsor

study and if applicable, referred for appropriate clinical care. Any participant experiencing a serious adverse event that the Principal Investigator believes to be related to study drug and a potential threat to the health and safety of the participant or fetus will be withdrawn from the study (see section 8.1).

#### 4.4.2. Data Collection and Follow-up for Withdrawn Participants

We will make a strong effort (via phone calls and alternative contact information) to obtain follow-up information on all participants who are prematurely withdrawn from the project.

## 5. Study Drug

Bupropion is an antidepressant medication for oral administration approved in the United States for the treatment of Major Depressive Disorder, Seasonal Affective Disorder and Smoking Cessation in adults. For more detailed information, see section 1.2 (Investigational Agent).

### 5.1. Description

Bupropion for this study is supplied as commercial SR 150mg tablets. The placebo will be supplied as over-the-counter calcium carbonate 648mg tablets which are nearly identical in size, shape and color to the active bupropion product.

### 5.2. Treatment Regimen

Participants will be randomized to receive Bupropion or placebo, to begin after completing the Baseline visit according to the regimen in Table 1 below.

### 5.3. Method for Assigning Participants to Treatment Groups

Participants will be randomly assigned to one of two treatment conditions: Bupropion 300 mg/day (n = 180) or placebo (n = 180). We will use small-block randomization by site (Penn or MATER) provided by [name], the study biostatistician. A PHQ-9 score of 10 or greater will be used to identify major depression and stratify the randomization on it. Study site (Penn or MATER) will be the second of the two stratification variables. Study staff and the Investigational Drug Service (IDS) staff will be responsible for medication randomization. The process for randomization is: 1) The research coordinator will complete a “randomization form,” which includes the variables to be entered into the randomization program and fax or email the form without protected health information to the UPenn site; 2) A designated study staff member

Table 1: Medication Dispensing Schedule

	Medication Dispensed For	Morning Dose	Evening Dose	Total Daily Dose
Visit A: Screening	N/A	No medication	No medication	
Visit B: Baseline	Wk 1	150 mg	No medication (for first 3 days); then 150 mg	150 mg
Visit C: Wk 1	Wk 2 through Wk 5	150 mg	150 mg	300 mg
Visit D: Wk 3	N/A	N/A	N/A	N/A
Visit E: Wk 5	Wk 6 through Wk 10	150 mg	150 mg	300 mg
Visit F: Wk 7		150 mg	150 mg	300 mg
Visit G: Wk 10	Endpoint	No medication	No medication	N/A

CONFIDENTIAL

This material is the property of the University of Pennsylvania. Do not disclose or use except as authorized in writing by the study sponsor

Visit H: Wk 24 Post-TQD	N/A	No medication	No medication	N/A
Visit I: 2 wk postpartum	N/A	No medication	No medication	N/A
Visit J: 6 wk postpartum	N/A	No medication	No medication	N/A

at the UPenn site will enter the variables into the randomization program, which will assign a randomization group to the participant; 3) the designated study staff member will fax the participant's randomization group to IDS, which will assign a kit number to the participant and fax the kit assignment to the research coordinator; 4) the research nurse or physician will dispense medication to the participant and complete and sign the IDS prescription form included in the starter kit; 5) The research coordinator will fax the completed form to IDS. The medication will be dispensed using the above dosing schedule. To maintain double-blind conditions, study staff responsible for randomization will not be involved in the recruitment of participants, study visits, or data collection. IDS will provide each study site a supply of starter kits to use for initial study medication dispensing.

Study drug for subsequent visits will be ordered by the research coordinator using the "Research Pharmacy Schedule" form, a copy of which will be retained in the participant's research file. The study drug will be ordered at Baseline Visit B for Weeks 2-5 and Target Quit Day Visit C for Weeks 6-10. The study drug will be picked up at IDS and brought to the study visit. If the participant is unable to attend the scheduled study visit the study drug will be stored at the Treatment Research Center in the Medication Room. Study drug will be dispensed at three time points during the study: Baseline (Visit B: 1 week of medication), Target Quit Date (Visit C: 4 weeks of medication), and Week 5 (Visit E: 5 weeks of medication). The initial dispensing will be done directly by the research nurse or physician, who will ensure that the patient understands the medication regimen. Study medication will be dispensed by the research nurse, physician, or research coordinator (trained and supervised by the nurse or physician), who will assess each participant for study medication AEs, documenting and reporting them as required. Participants with severe psychological symptoms or determined to be inappropriate for the study by an investigator will be withdrawn from the study. A study nurse or physician will follow participants withdrawn completely from treatment until they are referred for appropriate clinical care. For research purposes, and with the participant's continued approval, we will collect data at all subsequent time points until the 24 weeks post-TQD visit.

#### **5.4. Preparation and Administration of Study Drug**

**5.4.1 Chemistry and Manufacturing:** Bupropion sustained-release 150mg tablets will be purchased commercially, as round white tablets with only an imprint. An over-the-counter calcium supplement in tablet form, with similar shape and color, will be used as the 'placebo' for bupropion tablets in this clinical trial. Medication will be prepared at the University of Pennsylvania, Investigational Drug Service, [name].

**5.4.2 General Method of Preparation and Packaging:** The Investigational Drug Service will purchase Bupropion sustained-release 150mg tablets (made by Watson Laboratories) from a pharmaceutical wholesaler. These tablets were selected because they are round, white and have an imprint on only one side of the tablet.

The tablets will be used without alteration. For dispensing to study participants, they will be packaged in blister cards with the imprint facing the foil, so that members of the research team cannot see the imprint side of the tablet.

CONFIDENTIAL

This material is the property of the University of Pennsylvania. Do not disclose or use except as authorized in writing by the study sponsor

## **5.6 Packaging**

The Investigational Drug Service of the University (IDS) of Pennsylvania will package bulk drug on-site, containing medication in blister packaging. Medication will be dispensed in amounts as described in Study Procedures (below).

## **5.7 Blinding of Study Drug**

All participants and research staff will be blinded as to whether the participant is in the bupropion or placebo group until the end of the study once the decision to break the study blind is determined (after study database lock). Codes linking randomization number for each participant to actual treatment will be secured in a sealed, opaque envelope and maintained in a locked drawer in the research pharmacy and the hospital pharmacy. Research participants will be given the emergency contact number for the study during the consenting process.

See section 8.4 (Unblinding Procedures) for a description of the process for unblinding a study participant.

# **6. Study Procedures**

[figure not shown]
## **6.1 Recruitment**

We will distribute IRB-approved recruitment materials (i.e. brochures, post cards and posters) to recruit women who smoke and wish to quit smoking through participation in the trial. We will work with Jefferson and Penn OB clinics to access EPIC to identify pregnant smokers receiving prenatal care and, working with their obstetrician, invite them to consider study participation.

We will ask clinicians for permission to mail IRB-approved recruitment materials to their patients, who have reported recent smoking behavior and may meet study inclusion criteria based on EPIC screening. We will also advertise in media, including online classifieds such as Craigslist, newspapers (print and online), magazines, radio, and social media. We will use Facebook and Instagram to post study recruitment ads, including pictures and texts. Interested individuals can click a link that will redirect them to the recruitment landing page. The landing page will ask interested participants to fill in information—including name, phone number, pregnancy status and smoking status—to determine whether they are eligible. The landing page will be housed on a secure web server that is encrypted and password protected with different levels of user access and privileges. The web server—our Data Management Unit (DMU)—is flexible and ensures data quality and security (see appendix).

CONFIDENTIAL

This material is the property of the University of Pennsylvania. Do not disclose or use except as authorized in writing by the study sponsor

We will post and distribute recruitment material in community settings with public posting areas or other means of providing community access to materials (such as town halls, public libraries, YMCAs, health fairs). We will obtain permission at select locations before distributing or posting the approved recruitment materials (ensuring compliance with other institutions guidelines, including seeking IRB approval as needed to conduct recruitment activities). We will also encourage referrals from clinicians in the surrounding areas at each site including Penn Family Medicine. At the Jefferson site, we will recruit patients from MATER (Maternal Addiction, Treatment, Education and Research, which provides methadone maintenance treatment for pregnant women), part of the Pediatrics Department. MATER is located at [name], which is where recruitment will take place and treatment will be delivered. We will also recruit patients from Jefferson University Department of Obstetrics and Gynecology Associates (JOGA). We will conduct a brief in-person pre-screening questionnaire and a screening interview over the phone or in-person at the participant's obstetrics clinic to assess study eligibility criteria. At Jefferson, medical records will be reviewed for gestational age and smoking status to identify prospective participants. Prospective participants who appear to meet eligibility criteria for the study will be scheduled for an in-person Informed Consent and Screening visit. See Table 2 below for the schedule of assessments. Buprenorphine-treated women will be recruited through the Penn and Jefferson MATER sites as described above.

CONFIDENTIAL

This material is the property of the University of Pennsylvania. Do not disclose or use except as authorized in writing by the study sponsor

## 6.2 Visit A: Informed Consent and Screening (Approximately 60 minutes, in-person)

In a private setting, each participant will receive a description by a study staff member of the study protocol, its risks, potential benefits, and alternative treatments available. Following resolution of any questions, participants who appear to understand the nature of the study and consent will be asked to sign the study consent form. We have created two informed consent forms (ICFs), one for Penn and one for Jefferson, to address site-specific differences. An entire copy of the ICF will be given to each participant, who will be reminded that the consent expresses her willingness to participate but that the subsequent screening process will determine final eligibility. Further, she will be reminded that participation is voluntary, and at any time, she may withdraw from the study. Following the informed consent process, a research coordinator will obtain demographic information, administer a reading test (SORT), and extract information from the patient's medical record (including medical history and medications, obstetric history, blood pressure, and weight), and perform a psychiatric diagnostic interview (MINI; sections A through K) the PHQ-9 to differentiate depressed and non-depressed women for randomization, and a Timeline Follow-back smoking interview covering the preceding 30 days. We will also measure breath CO at this and every subsequent visit.

The participant will also be asked to provide locator information. Selection of follow-up locators is particularly important for the successful tracking of patients for follow-up evaluations. Study staff will select patient locators on the basis of relationship to client, duration and current status of relationship, frequency of contact with the patient, and willingness to participate. Locators are contacted when efforts to reach a patient are unsuccessful, which contributes both to maintaining patients in treatment and enhancing data collection. Participants will be asked for one or two locators.

The initial assessment in the clinic will help to exclude ineligible participants, facilitate clearance by an obstetrician for any medical condition that requires approval (e.g., mild hypertension), and ensure that the woman's gestational age is 13-26 weeks. Gestational age will be assessed for enrollment purposes based on the method used by the NICHD-sponsored Maternal-Fetal Medicine Units Network. The gestational age will be based on the projected estimated date of delivery (EDD), as determined by U/S and the last menstrual period (LMP; see below). Because the project EDD depends on information from the earliest dating U/S, if no U/S has been performed previously, one will be performed to determine eligibility. The EDD also requires that the first day of the LMP be determined and a judgment made as to whether or not the participant has a "sure" LMP.

- If the LMP date is uncertain, the U/S measurements obtained at the participant's first U/S will be used to determine the projected gestational age, by the standard method used at the recruitment site.
- If the date of the LMP is certain and the U/S confirms the gestational age within +/- 7 days, the LMP-derived gestational age will be used to determine the project gestational age.
- If the U/S-determined gestational age does not confirm the LMP-generated gestational age within +/- 7 days, the U/S will be used to generate the project gestational age.

Thus, all participants will be assigned a project EDD and gestational age when they are evaluated for enrollment. An U/S machine is available at each recruitment site and results will be supervised and reviewed by [name] (Penn) or [name], M.D. (Jeff).

CONFIDENTIAL

**6.3 Visit B: Baseline (Pre-quit) (Approximately 90 minutes, in-person or divided between in-person and telephone sessions)**

Although this session requires an in-person visit, part of the session may be completed via telephone. The session must be completed 1-30 days after completion of the screening visit. At the in-person visit, we will measure breath CO level and draw three tubes (i.e., 21 cc) of maternal blood to assess NMR and provide DNA for genotyping. Blood will be stored in a coded manner in a designated -80° freezer and shipped on dry ice to the laboratory of [name] at the University of Toronto approximately every four months throughout the study. Samples from both sites will be shipped from their storage location at Penn (see section 9.5) and will follow the guidelines for shipping international biological samples as required by the university.

Table 2: Study Assessments

	Visit A	Visit B	Visit C	Visit D	Visit E	Visit F	Visit G	Visit H	Visit I	Visit J
	Screen	Baseline (Pre-quit)	Wk 1 (TQD)	Wk 3	Wk 5	Wk 7	Wk 10	Wk 24	Wk 2 PP	Wk 6 PP
ICF with HIPAA	X									
Medical record review	C									
Med History Questionnaire	X									
Demographics	X									
SORT	X									
MINI 	X				X 		X 			
TLFB (preceding 30 days)	X									
Gestational Age	X, C									
Blood sample: DNA, NMR		X								
Breath CO*	X	X	X		X		X	X 		
Dispense medication		X	X		X					
Text messaging		Daily	Daily	Daily	Daily	Daily	Daily			
Assessment of AEs and medication adherence		X	X	T	X	T	X			
Weight, blood pressure	X or C	C	C	C	C	C	C			
Pulse		X	X		X		X			
ACE questionnaire		X or T								
Smoking History Questionnaire		X or T								
FTND		X or T								
BISS		X or T								
WEAQ		X or T								
PHQ-9	X	X or T	X	T	X	T	X	X	T	T
QSU		X or T	X		X		X			
MED-Q							X			
TLFB (since last visit)		X or T	X	T	X	T	X	X	T	T

CONFIDENTIAL

This material is the property of the University of Pennsylvania. Do not disclose or use except as authorized in writing by the study sponsor

Smoking cessation counseling (30 min)		X							
Smoking cessation counseling (20 min)			X						
Smoking cessation counseling (10 min)				T	X			T	T
Blood sample: [bupropion, hydroxybupropion]					X				
Birth outcome data								C	

TQD: target quit date; PP: postpartum; ICF: informed consent form; HIPAA: Health Insurance Portability and Accountability Act; Assessments: X=in-person; X=MINI sections A through K will be administered. X=Only MINI section B (Suicidality) will be administered; X=in-person only; T=by telephone; C=chart review; SORT: Slosson Oral Reading Test; MINI: Mini-International Neuropsychiatric Interview; TLFB: Timeline Follow-back Interview for cigarettes smoked; NMR: nicotine-metabolite ratio; [CO]: carbon monoxide concentration; AEs: adverse events FTND: Fagerstrom Test for Nicotine Dependence; BISS: Body Image State Scale; PHQ-9: Patient Health Questionnaire-9; WEAQ: Weight Efficacy After taken Quitting survey; QSU: Questionnaire of Smoking Urges; MED-Q: medication group question; \*CO readings may also be at the time of delivery and at the time of the post-partum office visit

An in-person or telephone interview will be used to obtain background information for use as potential covariates and to assess the study's external validity [including smoking history (e.g., age at initiation, past use of nicotine treatments, current rate, menthol vs. regular tobacco, presence of other smokers in the home), obstetrical history to confirm and augment information obtained from review of the medical record (number of pregnancies, pregnancy outcomes), and medical and psychiatric history (with current medications extracted from the medical chart). Sessions in which the assessments are conducted by telephone, the telephone interview should be completed prior to the in-person visit.

Nicotine dependence severity will be assessed with the Fagerstrom Test for Nicotine Dependence, a validated 6-item measure (144). We will measure depression symptom score using the PHQ-9 (145) and will use a score of 10 or more to differentiate depressed and non-depressed women. This cut point will enable us to use depression as a stratification variable and potential mediator. Craving severity, which has been related to long-term cessation in cessation trials (147), will be measured with the 10-item brief Questionnaire of Smoking Urges (QSU; 146). The QSU contains 2 subscales (anticipation of reward, relief from negative affect).

Weight concerns will be measured using the Weight Efficacy After Quitting survey, a 6-item validated scale that assesses general and smoking-specific weight concerns (148). We will also use the Body Image States Scale (BISS) (149), a 6-item measure of evaluative and affective experiences of one's physical appearance. Body image may be a more potent moderator of smoking cessation treatment effects (and such concerns are particularly relevant in pregnant women). A single item in the smoking history questionnaire will assess the number of smokers in the home. The Adverse Childhood Experiences (ACE) questionnaire, a 10-item self-report measure will be administered at this time as well.

Following the assessments, participants will receive the first session of manual-based counseling from a coordinator that is trained and supervised by [name]. The counseling protocol is based on Public Health Service guidelines for smoking cessation treatment (12) and is intended to enhance study retention and ensure that participants in the placebo arm receive active treatment to quit smoking. The 30-minute, "pre-quit" counseling session will prepare for the target quit day (TQD). This session focuses on reviewing the participant's history and experience with quitting, beliefs about smoking and quitting, and perceived barriers to cessation. The participant will receive a one-week supply of study medication and the nurse or physician will review with the participant instructions for taking the study medication, which include instructing the participant to begin taking the medication on the following morning. Study staff will complete a baseline adverse event checklist, an open-ended evaluation of any existing symptoms using the established study checklist of adverse events, before the subject begins taking the study medication.

CONFIDENTIAL

Upon initiation of the medication, subjects will begin to receive daily text messages describing the progress of their pregnancy and reminding them to take their medication. The text messaging will continue throughout the 10-week medication treatment period. The greatest impact of this approach has been seen with interventions that include personalized text message reminders and interactivity (105). Personal tailoring will involve: 1) flexibility in the timing of receipt of messages each day (“set time” chosen by the woman) and 2) day-by-day facts, tips, suggestions, and benchmarks appropriate to each stage of fetal development calculated using the woman’s estimated date of delivery. The morning message will consist of 2 components: a “hook” text that details the fetus’ development and pregnancy tips and a “prompt” text reminding the subject to take her medication at the prescribed times. We will use a database of messages consisting of SMS text and rules to determine which message to send based on gestational age, time of day, and the participant’s previous replies. An example morning message is:

*Your baby’s heart is now developed. Remember to take your study medication with your morning and evening meals.*

The evening message will ask participants whether they took their study medication as prescribed:

*Did you take the study medication as prescribed today?*

*Reply*

*"1" for Yes, I took it today*

*"2" for No, I did not take it today*

If participants do not respond to the evening message within 1 hour, a reminder message will be sent (“*Did you take your study medication as prescribed today. REPLY "1" for Yes, I took it today; "2" for No, I did not take it today.*”). A maximum of three text messages will be sent in a given day.

All participants will be offered a free cell phone with unlimited talk and text for up to 32 weeks of study participation to allow them to receive the text messages, participate in phone counseling and to contact study personnel. Participants have the option to refuse the phone. They will be asked to return the phone to the study staff at the end of the study. They will be paid \$20 for returning the phone. Participants will not be responsible for the cost of lost or stolen phones. We will replace a lost or stolen phone once during the study.

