### **Potential Risks**

The most common adverse events associated with bupropion when used for smoking cessation are dry mouth (11%), insomnia (31%) and dizziness (8%).

Frequent adverse reactions (occurring in at least 1% of patients) include rhinitis, neck pain, allergic reaction, hot flashes, hypertension, increased appetite, anorexia, constipation, arthralgia, myalgia, tremor, somnolence, thinking abnormality, bronchitis, pruritis, rash, dry skin, urticaria, taste perversion, asthenia, fever, headache, dyspepsia, vomiting, agitation, depression, irritability sweating, blurred vision or diplopia, and urinary frequency (Zyban Package Insert).

Infrequent adverse reactions (occurring in less than 1% but greater than 0.1% of patients) include: chills, inguinal hernia, photosensitivity, flushing, migraine, postural hypotension, stroke, tachycardia, vasodilation, abnormal liver function, bruxism, dysphagia, gastric reflux, gingivitis, jaundice, stomatitis, ecchymosis, edema and peripheral edema, leg cramps and twitching, abnormal coordination, CNS stimulation, confusion, decreased libido, decreased memory, depersonalization, emotional lability, hostility, hyperkinesia, parkinsonism, hypertonia, hypesthesia, paresthesia, suicidal ideation, and vertigo, accommodation abnormality and dry eye, polyuria, and urinary urgency (Zyban Package Insert).

Rare adverse reactions (occurring in less than 0.1% of patients) include: malaise, syncope, amnesia, ataxia, derealization, hypomania, and bronchospasm (Zyban Package Insert).

Bupropion is contraindicated in patients with a history of seizure disorder or in patients with a current or prior diagnosis of bulimia or anorexia, because of a higher incidence of seizures in these individuals when treated with bupropion.

Patients taking bupropion for smoking cessation have experienced mood changes, including depression or mania, psychosis, hallucinations, paranoia, delusions, homicidal ideation, hostility, agitation, aggression, anxiety, and panic, as well as suicidal ideation, suicide attempt, and completed suicide.

Abuse potential: Bupropion is not likely to be reinforcing to users of stimulants, including amphetamines. Abuse of bupropion by inhalation or injection of crushed tablets have been reported, resulting in seizures and/or death.

The risk of bupropion for smoking cessation in pregnant women has not been adequately evaluated. There is a risk that bupropion could adversely affect the developing fetus.

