6. Current unstable medical problems or potential inability to tolerate study treatment [e.g., threatened abortion: current persistent hyperemesis gravidarum (HEG) requiring intravenous fluids (to be rescreened when HEG is stabilized/resolved and no electrolyte abnormalities are evident); hypertension with evidence of end organ dysfunction or on more than 2 medications at the start of the pregnancy]; arteriovenous malformation; AIDS; laboratory evidence of hepatic impairment (e.g. viral hepatitis with serum transaminase levels more than twice the upper limit of normal) ; renal impairment (e.g., elevated creatinine or creatinine clearance <75cc/hr), metabolic disorders (e.g., hypoglycemia, hyponatremia) or end organ damage from any chronic medical condition (e.g. abnormal pulmonary function tests), glaucoma, or other significant medical problems that in the opinion of a study obstetrician makes the risk of study participation unacceptable.
  7. Known major fetal congenital malformation—as determined by the study obstetrician—diagnosed prior to study randomization
  8. History of seizure disorder
  9. Current use of a smoking cessation medication in addition to the study medication, such as nicotine replacement therapy
  10. Current or history of bulimia or anorexia nervosa
  11. Current use of tobacco products other than cigarettes (e.g., E-cigarettes)
  12. Current clinically significantly abnormal laboratory evaluations that are not adequately controlled by standard of care treatment.
  13. History of severe head injury (i.e., with loss of consciousness)
  14. Any medical condition or concomitant medication that could compromise subject safety or treatment, as determined by the Principal Investigator and/or Study Physician.
  15. Inability to provide informed consent or judged by the Principal Investigator and/or Study Physician to be an unsuitable candidate for a clinical drug trial.

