## **8.6 Protection of Participants**

Complementing the safety measures noted above, additional procedures will be followed to protect the safety of the research participants. Potential participants will be screened for medical illnesses that would preclude the use of bupropion. Participants selected for the study will be evaluated regularly while receiving study drug treatments, both by study staff at periodic visits (as described in Table 2) and by obstetrics staff for their routine prenatal monitoring. AEs will be monitored regularly in-person or by telephone (see Table 2) and a study physician will be available at all times to evaluate and treat adverse effects of the medication. The participants' weight and blood pressure will be monitored during their standard prenatal visits and pulse rate will be measured at all in-person visits (see Table 2). AEs that reflect significant risk to the participant or fetus will result in discontinuation of the study medication, a decision that will be made by the site principal investigator together with the study obstetrician at that site. Venipuncture will be carried out with good aseptic technique by an experienced phlebotomist, nurse, or physician. Venipuncture sites will be monitored carefully for signs of infection. Participants will be given a 24-hour emergency number that they can call if necessary. The physician or nurse will clinically follow all participants who are discontinued due to a serious AE until the AE resolves and becomes completely stable, unless a referral to another physician (i.e., a specialist) is clinically indicated or requested by the participant.

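### From baseline to week 10, blood pressure comes only from routine prenatal charts with no rule on how recent the reading must be, so the week-1 entry may predate the first dose.

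*Combined protocol and SAP*

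**What the plan says.** Table 2 in Section 6.3 lists "Weight, blood pressure" as a scheduled assessment. The entry is X or C at screening and C alone at Visits B to G; the key to the table gives "C=chart review". The pulse row has X (in person) at Visits B, C, E and G.

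Section 8.6 shows that the split is intended: the participants' "weight and blood pressure will be monitored during their standard prenatal visits and pulse rate will be measured at all in-person visits". At screening, Section 6.2 has the coordinator "extract information from the patient's medical record (including medical history and medications, obstetric history, blood pressure, and weight". The visit text for weeks 1, 5 and 10 (Sections 6.4, 6.6 and 6.8) mentions no blood pressure measurement.

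On timing, Section 6.3 describes "instructing the participant to begin taking the medication on the following morning", and Section 5.3 lists the first dispensing as "Baseline (Visit B: 1 week of medication", so Visit C falls about seven days after Visit B. The dose step described in the Study Summary, after three days, also falls in that week.

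On risk, Section 1.5 (Potential Risks) includes hypertension among reactions seen in at least 1% of patients: "allergic reaction, hot flashes, hypertension, increased appetite". Section 4.2 excludes only "hypertension with evidence of end organ dysfunction or on more than 2 medications at the start of the pregnancy", so some women with treated hypertension can enroll. Section 6.2 provides for an obstetrician to clear conditions such as mild hypertension.

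**The concern.** Table 2 appears to give a blood pressure value for each study visit, but the value is whatever the prenatal clinic last recorded. Nothing ties prenatal appointments to the first dose, to the dose step or to study visits. No reading date is required.

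Week 1 is the most exposed point because so few days separate the first dose from Visit C. Visit B is also chart-only, so the baseline and week-1 entries can be the same reading, which shows no change whatever the drug has done.

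What is at stake is early detection of a reaction that the protocol itself names, in pregnant women, some of them already hypertensive. The adverse-event route is weak for a rise without symptoms. In Section 10.1, blood pressure is not among the 39 checklist items. It appears only in the open-ended list, where moderate is Code 2 and severe is Code 3. Severity is graded by how far an event limits activity, so a silent rise would be graded mild, and no code is listed for mild. The instruction printed above the checklist, if it also governs the open-ended list in the same table, then requires no report unless the woman asks for the study physician.

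**Working it through.** The plan states no figure on this point, so there is none to reproduce. The check asks how often a woman would have no on-drug reading in her chart at a given study visit.

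**Inputs**
- First dose: the morning after Visit B, day 1 (Section 6.3).
- Study visits, in days after Visit B: C = 7, D = 21, E = 35, G = 70 (Table 2; supplies of one, four and five weeks in Section 5.3).
- Interval I between prenatal appointments: not in the documents. Assumed 14, 21 or 28 days, with 7 and 42 as outer cases.
- Assumed: appointments are evenly spaced, kept, and unrelated to study dates.

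**Formula.** At a visit d days after Visit B, d − 1 days have passed since the first dose. The chance that no appointment fell in that time is max(0, 1 − (d − 1)/I).

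| Visit | d − 1 | I = 14 | I = 21 | I = 28 |
|---|---|---|---|---|
| C, week 1 | 6 | 1 − 6/14 = 57% | 1 − 6/21 = 71% | 1 − 6/28 = 79% |
| D, week 3 | 20 | 0% | 1 − 20/21 = 5% | 1 − 20/28 = 29% |
| E, week 5 | 34 | 0% | 0% | 0% |
| G, week 10 | 69 | 0% | 0% | 0% |

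**Sensitivity**
- Weekly appointments: 1 − 6/7 = 14% at week 1, or 0% if a full seven days on drug are counted. With appointments aligned to study visits the problem disappears.
- A 42-day interval: 1 − 6/42 = 86% at week 1, 1 − 20/42 = 52% at week 3, 1 − 34/42 = 19% at week 5, and 0% by week 7.
- Counting seven days instead of six at week 1 gives 50%, 67% and 75% for I = 14, 21 and 28. This is also the chance that no appointment fell between Visits B and C, so that both entries rest on one reading.
- The three-day visit window in Section 6.12 puts Visit C at day 4 to 10. For I = 14 the week-1 figure runs from 1 − 3/14 = 79% to 1 − 9/14 = 36%; for I = 28, from 1 − 3/28 = 89% to 1 − 9/28 = 68%.

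**Readings over the ten weeks.** 70/14 = 5.0, 70/21 = 3.3 and 70/28 = 2.5 per woman. With readings this sparse, a rise that comes and goes between appointments can leave no trace.

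**The case against.** The strongest reply is that other routes exist and that the gap closes quickly. Section 3.2 also draws adverse effects from regular obstetrics visits. Section 8.2 has staff ask about events at every contact and examine where appropriate. Section 8.6 has obstetrics staff following the women while on drug. Section 10.1 has the study team regularly review the prenatal record, which is fully abstracted at delivery. A charted reading can lead to the coded event for raised blood pressure, even though staff did not take it. Section 4.2 also lets a study obstetrician exclude a woman whose risk is judged unacceptable.

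This stands against two stronger readings. A reader might infer that a drug-related rise would simply be missed. The documents do not support that: on the same formula every woman has an on-drug reading by week 5 at intervals up to 28 days, and obstetric care should show a sustained rise. A reader might also infer that pre-dose readings dilute a difference between arms. Sections 7.1 and 7.2 specify no comparison of blood pressure values by arm; H2 tests the frequency of moderate-to-severe adverse events.

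It can also be said that C might mean only readings since the last visit, and that Section 9.3 provides a not-done entry. The plan does not say which is meant. On that reading the same women would have a blank at week 1 in place of a pre-dose value, and still no on-drug measurement.

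Finally, the percentages depend on an interval and an independence that the documents do not give. Recruitment runs through obstetrics clinics, so some alignment is possible. That limits the size of the point but does not supply the missing recency rule.

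**Conclusion.** The point holds as a gap in early safety measurement. Blood pressure from baseline to week 10 is chart-only, with no recency or date rule, and the week-1 entry may predate the first dose. The size is about 57%, 71% or 79% of women at prenatal intervals of 14, 21 or 28 days unrelated to study dates, and near zero if appointments are weekly or aligned. By week 5 it is zero at intervals up to 28 days.

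The consequence is that a rise soon after starting drug may be detected late, and a short-lived or symptomless one may be missed. Neither the abstinence analysis nor the stated power is affected. The change is worth making because it is cheap and concerns a reaction that the protocol names.

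**What to change.** - In Table 2, change blood pressure from C to X at in-person Visits B, C, E and G, measured and dated with the pulse. Bring Sections 6.3, 6.4, 6.6, 6.8 and 8.6 into line.
- Keep chart review for the telephone visits (D and F) and for any visit not held in person. Record the date of each chart reading, and do not count a reading from before the first dose as on-treatment.

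At attended visits each woman then has a pre-dose value and on-drug values at weeks 1, 5 and 10, and the share of week-1 values that predate the first dose falls to zero. The cost is a cuff reading of a few minutes at four visits that already take place, plus one date field on the case report form. Dating chart readings alone would show which values predate dosing but would not supply the missing week-1 measurement. No threshold or management rule is proposed here.
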